1.0 Objectives

1.1 Study Objectives

The long term goal of this project is to determine the likely health effects of very low nicotine content in cigarettes, in conjunction with availability of nicotine-containing electronic cigarettes (e-cigs) among smokers with mental health conditions (SMHC). This will be tested in a rigorous randomized controlled trial design. We plan to use a comprehensive set of measures of proven validity and reproducibility, including toxicant exposure, addiction and mental health to assess these effects. The specific objective of this study is to recruit a cohort of 240 current exclusive daily SMHC (diagnosed using the MINI International Neuropsychiatric Interview) and to measure a comprehensive battery of behavioral and health indicators at 4 and 8, 12 and 16 weeks after being randomized to use either normal nicotine content (NNC) Spectrum cigarettes (11.6 mg nicotine/cigarette) or very low nicotine content (VLNC) Spectrum cigarettes (0.2 mg nicotine/cigarette) while also having access to a JUUL e-cig (JUUL Labs, Inc.) containing either 0% or 5% nicotine strength e-liquids in a randomized double-blind, placebo-controlled 2 by 2 design. Our central hypothesis is that key markers of harms to health (e.g. urinary NNAL, exhaled CO, measures of addiction, and mental distress) will be significantly improved among SMHC who are provided very low nicotine cigarettes and high nicotine e-cigs. Study aims are:

Aim 1: To determine whether SMHC have lower levels of markers of harm (e.g. urine NNAL, exhaled CO, measures of mental health) and cigarette addiction when switched to VLNC cigarettes, as compared with NNC cigarettes, at the end of the randomized phase (week 16).

Aim 2: To determine whether SMHC have lower levels of markers of harm (urine NNAL, exhaled CO) and cigarette addiction when provided with nicotine-containing versus zero nicotine electronic cigarettes, at the end of the randomized phase (week 16).

Aim 3: To determine whether use of VLNC cigarettes increases the proportion of smokers who completely switch away from combustible tobacco use (no cigarette use in the past 7 days and CO < 6ppm), as assessed (a) at the end of the randomized phase (week 16) and (b) 4 weeks after the end of the randomized phase of the trial (week 20), compared to those using NNC cigarettes.

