1.3 Secondary Study Endpoints

Secondary endpoints include exhaled CO, Kessler-6 score, and cigarette/e-cigarette dependence using Penn State Cigarette Dependence Index (PSCDI) and Penn State Electronic Cigarette Dependence Index (PSECDI), at week 16, and cigarette abstinence (no cigarette use in the past 7 days and CO < 6ppm) at week 20.

Additional endpoints include:

Health effects and toxicant exposure measures: Pulmonary Function Tests (PFT), Clinical COPD Questionnaire (CCQ), urinary CYMA (biomarker for acrylonitrile [volatile organic compound] exposure), 3HPMA (biomarker for acrolein [volatile organic compound] exposure, cotinine (biomarker of nicotine exposure)

Mental health measures: Center for Epidemiological Studies-Depression (CES-D), Overall Anxiety Severity and Impairment Scale (OASIS), Quick Inventory or Depressive Symptomatology (QIDS), Perceived Stress Scale (PSS)

Nicotine/Tobacco use and addiction measures: daily cigarette use, daily e-cig use, Fagerstrom Test for Nicotine Dependence (FTND), Hooked on Nicotine Checklist (HONC), , Minnesota Nicotine Withdrawal Scale (MNWS)

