(VOCs). The health effects of heated and aerosolized constituents of e-cig liquids, including solvents, flavors, and toxicants, are not completely understood.(19) However, some studies suggest e-cigs, when used exclusively, have a more favorable toxicity profile than tobacco cigarettes.(20, 21) E-cigs have become increasingly popular among cigarette smokers, particularly SMHC. For example, in the PATH Wave 1 survey, cigarettes plus e-cigs was by far the most common pattern of combined use.(2) In a large population survey from 2015, people with a mental health condition were twice as likely to be current cigarette smokers and twice as likely to be current e-cig users as people without a mental health condition.(14) This study aims to assess the likely health effects of a product standard lowering the nicotine content of cigarettes in SMHC when having access to e-cigs.

It is highly likely that in a scenario in which FDA issued a product standard requiring only very low nicotine content in cigarettes, existing smokers may attempt to supplement their nicotine from alternative sources. Given the current prevalence of e-cig use among current and former smokers, they are a prime candidate for such a source. To date, most studies designed to evaluate the likely effects of a low nicotine product standard for cigarettes have required participants to only use the specially designed reduced nicotine content cigarettes without supplementation from their own cigarettes or any other nicotine sources.(4, 8) This was a reasonable research design, however it has become clear that a significant proportion of those allocated to smoke only VLNC cigarettes were non-compliant, as their cotinine concentrations could not realistically be obtained from smoking only VLNC cigarettes.(22, 23) It seems most likely that the participants “topped off” their nicotine levels by occasionally smoking normal nicotine cigarettes. In the real world, if a product standard requiring only VLNC in cigarettes were to be implemented it is likely that alternate nicotine products, such as e-cigs, would also be available, so it is important to examine the patterns of product use and the resulting effects on biomarkers of toxicant exposure in that situation.

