7.4.3 Method for Assigning Subject to Treatment Groups

Eligible participants will be allocated to one of the four conditions using a blocked randomization with a 1:1:1:1 ratio of condition assignments via REDCap. The randomization table will be created by the study statistician and only unblinded staff will have access to it.

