7.4.4 Subject Compliance Monitoring

Compliance will be monitored throughout the trial by a) daily product use logs; b) product accountability logs where the amount of product dispensed will be recorded and unused products collected and recorded; and c) questionnaires administered during study contacts regarding the use of other tobacco or nicotine products. Any problems that arise or are anticipated will be discussed and problem-solved with the coordinator. Furthermore, exhaled CO measurements will be collected throughout the study to verify smoking intensity and exposure levels.

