8.0 Subject Numbers and Statistical Plan

8.1 Number of Subjects

We plan to enroll 300 participants in order to randomize 240 participants (60 in each of the four study arms).

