8.2 Sample size determination

For the sample size calculation, we have used data for completers of our recent randomized controlled trial(8) to estimate magnitude of effects for the primary endpoint (NNAL, pmol/mg creatinine). Additionally, we have used data from Donny et al.'s trial [Table Supplement 15] (5). Based on their paper, the difference in log NNAL between the 0.4 mg/g group (sample size 96) and the 15.8 mg/g group (sample size 100) is $\log(0.78) = -0.248$ with a confidence interval of $\log(c(0.64, 0.96)) = (-0.446, -0.0408)$. Based on this, the within group standard deviation of log NNAL is 0.562. Combining the above two datasets, we shall assume that the effect size is 58% of the size of the standard deviation in the sample size calculation, slightly larger than reported above because our trial will have 16 weeks of follow-up. Let arm 3 of the trial be the group to which arms 1, 2 and 4 will each be compared. To adjust for multiple comparisons, the type one error level alpha is taken to be $.05/3=0.017$. The sample size of 60 subjects in each of the 4 arms is needed to provide 80% power of detecting a difference between any three arms and arm 3. In addition this trial will have over 95% power, at a 5% type 1 error rate, to detect the same effect on abstinence found in our recent RCT of VLNCs one month after the end of the randomized phase (20.2% in those randomized to VLNCs vs. 6.4% in those randomized to NNCs).

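### Aim 3 claims a complete switch away from combustible tobacco, but its rule counts only cigarettes and CO, so a cigar, pipe or hookah user with CO below 6 ppm scores as a success

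*Combined protocol and SAP*

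**What the plan says.** Section 1.1, Aim 3, compares VLNC with NNC cigarettes at weeks 16 and 20 on the proportion of smokers who "completely switch away from combustible tobacco use (no cigarette use in the past 7 days and CO < 6ppm". The bracket is the whole success rule.

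Section 1.3 lists as a secondary endpoint "cigarette abstinence (no cigarette use in the past 7 days and CO < 6ppm) at week 20". The rule is identical, but its label is narrower and it names week 20 only.

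Other tobacco use appears elsewhere, never as part of the outcome:

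- **Section 3.2, criterion 6:** use of a non-cigarette nicotine product (pipe, cigar and hookah among those named) in the 7 days before screening excludes a person.
- **Section 3.3.1:** such use reported at both Visit 2 and Visit 3 is a ground for withdrawal before randomization, judged case by case. The general withdrawal list, which covers the randomized phase, has no counterpart for cigars, pipe or hookah.
- **Section 7.2:** participants are asked to refrain from non-study tobacco and other smoked products, and at Visits 4-7 are asked what else they used.
- **Section 7.4.4:** compliance monitoring includes "questionnaires administered during study contacts regarding the use of other tobacco or nicotine products".

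Section 8.3 gives no separate definition of abstinence.

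**The concern.** The protocol separates cigarettes from other combusted products: sections 2.1 and 2.3 discuss a nicotine standard for cigarettes and for other combustible products, and the eligibility criteria name cigars, pipes and hookah as non-cigarette products. In Aim 3 the outcome is named for the wider class and scored on the narrower one.

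What is at stake is what may be concluded. A favourable result would support the statement that more VLNC participants stopped smoking cigarettes. It would not, as defined, support the statement that more of them left combustible tobacco, because movement to another combusted product is not scored as failure. Section 2.3 says the results are meant to inform FDA about a low nicotine standard, and for that purpose the two statements differ.

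**Working it through.** **1. Can a user of another combusted product pass the rule?** Take a participant at week 16 or 20 with no cigarettes in 7 days, some cigar, pipe or hookah use in those days, and CO below 6 ppm.

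| Source | Does it make this participant a failure on Aim 3? |
|---|---|
| 1.1, Aim 3 | No; both limbs are met |
| 1.3 | No; same rule, labelled cigarette abstinence |
| 3.2 and 3.3.1 | No; they act at screening or before randomization |
| 7.2, Visits 4-7 | No; use is asked about because it may affect biomarkers |
| 7.2, Visit 8 (COVID procedures) | No; the CO check follows a self-report about cigarettes only |
| 7.4.4 | No; used for compliance |
| 8.3 | No; no definition given |

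The participant is a success under the rule but has not done what Aim 3 names.

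**2. Are the data there to score it properly?** At week 16 (Visit 7), largely yes: other-product use is asked, though no recall period is stated. At week 20 (Visit 8) this is uncertain: the visit text speaks of cigarette and e-cig consumption, and section 7.4.4 does not list which contacts carry the other-product questions. The daily online survey between Visits 3 and 4 covers e-cig uses, cigarettes and non-study cigarettes, not other combusted products.

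**3. The plan's figures for this outcome.** Section 8.2 assumes "20.2% in those randomized to VLNCs vs. 6.4% in those randomized to NNCs". Section 8.1 plans "60 in each of the four study arms", so pooling over e-cig type gives 120 VLNC and 120 NNC.

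- Expected successes: 0.202 × 120 = 24.2 and 0.064 × 120 = 7.7, about 24 and 8.
- Section 8.2 states "over 95% power, at a 5% type 1 error rate, to detect the same effect on abstinence". With a pooled-variance normal approximation, two-sided 5%, mean rate 0.133:
 (0.138 × √120 − 1.96 × √(2 × 0.133 × 0.867)) / √(0.202 × 0.798 + 0.064 × 0.936) = (1.512 − 0.941) / 0.470 = 1.21, i.e. power 88.7%.

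The stated power is not reproduced. That is a separate matter, and nothing below rests on it.

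**4. Can the effect on the contrast be sized?** Let f_V and f_N be the fractions of scored successes in VLNC and NNC who used another combusted product. Then:

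- scored difference − difference under Aim 3's wording = 0.202 f_V − 0.064 f_N
- scored ratio ÷ ratio under Aim 3's wording = (1 − f_N) / (1 − f_V)

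The documents give neither fraction. Each reclassified participant moves a group's rate by 1/120 = 0.83 points. Assumed cases, starting from 24/120 v 8/120 (difference 13.3 points, ratio 3.0):

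| Assumed reclassified (VLNC, NNC) | Remaining successes | Difference | Ratio |
|---|---|---|---|
| 4 of 24, 0 of 8 | 20 v 8 | 10.0 points | 2.5 |
| 3 of 24, 1 of 8 (12.5% each) | 21 v 7 | 11.7 points | 3.0 |
| 0 of 24, 1 of 8 | 24 v 7 | 14.2 points | 3.4 |

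The scored contrast is overstated in the first case and understated in the third. In the second the ratio is unchanged and the difference is smaller. Nothing in the documents selects among them. In the first case z = 0.100 / √(0.1167 × 0.8833 × 2/120) = 2.41, two-sided p about 0.016, so even that case would not remove the contrast.

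**The case against.** The best defence is that this is a label, on a non-primary outcome, with little practical effect. The primary endpoint is NNAL. Section 1.3 already names the rule correctly. Participants enter as exclusive cigarette smokers, recent users of other products are screened out, and all are asked to refrain. CO is not specific to cigarettes: section 7.2 says other smoked substances may affect it, so the second limb will catch some of these users. All of this stands and argues for a low frequency. One limit is that section 7.2 suspends exhaled CO at visits while a mask restriction holds, so that safeguard is not always present at week 16.

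A reader might infer more: that the rule inflates the VLNC effect, since section 2.1 expects that "existing smokers may attempt to supplement their nicotine from alternative sources". The documents do not support that step. Section 2.1 goes on to name e-cigs as a prime candidate source, and suggests that earlier VLNC participants supplemented with normal nicotine cigarettes, which the rule already counts as failure. In the feasibility trial it describes, e-cigs were the most commonly chosen alternative in all groups. Every participant here receives an e-cig. The supply of VLNC cigarettes ends at Visit 7, which weakens the argument further at week 20. No section predicts a move to cigars, pipe or hookah.

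None of this repairs the mismatch. It shows that the mismatch is probably small in effect.

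**Conclusion.** The point holds as a mismatch between what Aim 3 claims and what its rule measures, and no other section resolves it. It is confined to Aim 3: in section 1.3 name and rule agree. No size or direction of bias can be given, because the rate of other combusted use among scored successes, and its split by arm, are not in the documents; the cases worked above are assumptions. A conclusion that the VLNC effect is overstated by some percentage would go beyond the evidence. So would one that the Aim 3 comparison is invalid: as a comparison of cigarette abstinence it stands. What does not follow from the rule as written is the wider conclusion about combustible tobacco.

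**What to change.** For Aim 3, at weeks 16 and 20, define success as no use of cigarettes or any other combusted tobacco product (cigar, pipe, hookah) in the past 7 days and CO below 6 ppm, scored from the other-product questions already asked. Confirm that an item with a past-7-day window is asked at both Visit 7 and Visit 8; Visit 8 is the one in doubt. The CO check at the remote Visit 8 can keep its trigger, since anyone meeting the wider rule also reports no cigarettes. Settle the definition before unblinding.

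Keep the section 1.3 cigarette-abstinence endpoint unchanged and report it alongside. It should not be justified as comparable with the earlier trial unless the cut-offs are checked: the quit outcome of that trial in section 2.2 was validated at CO below 9 ppm, and section 8.2 gives no cut-off for its rates.

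If the week 20 item cannot be confirmed, limit Aim 3's wording and conclusion to cigarette abstinence. That removes the contradiction but leaves the question about combustible tobacco unanswered.

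The cost is a change of wording and one questionnaire check, with no new visit or assay. The downside is a slightly lower success rate.

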1.2 Primary Study Endpoints

The primary endpoint for the study is urinary NNAL concentration at Week 16. Urine NNAL is a biomarker that provides an accurate estimate of recent exposure to the lung carcinogen, NNK.

1.3 Secondary Study Endpoints

Secondary endpoints include exhaled CO, Kessler-6 score, and cigarette/e-cigarette dependence using Penn State Cigarette Dependence Index (PSCDI) and Penn State Electronic Cigarette Dependence Index (PSECDI), at week 16, and cigarette abstinence (no cigarette use in the past 7 days and CO < 6ppm) at week 20.

Additional endpoints include:

Health effects and toxicant exposure measures: Pulmonary Function Tests (PFT), Clinical COPD Questionnaire (CCQ), urinary CYMA (biomarker for acrylonitrile [volatile organic compound] exposure), 3HPMA (biomarker for acrolein [volatile organic compound] exposure, cotinine (biomarker of nicotine exposure)

Mental health measures: Center for Epidemiological Studies-Depression (CES-D), Overall Anxiety Severity and Impairment Scale (OASIS), Quick Inventory or Depressive Symptomatology (QIDS), Perceived Stress Scale (PSS)

Nicotine/Tobacco use and addiction measures: daily cigarette use, daily e-cig use, Fagerstrom Test for Nicotine Dependence (FTND), Hooked on Nicotine Checklist (HONC), , Minnesota Nicotine Withdrawal Scale (MNWS)

2.0 Background

2.1 Scientific Background and Gaps

Tobacco use remains the single biggest cause of preventable morbidity and mortality in the United States,(1) and cigarettes are by far the most commonly used tobacco product. For example, among all adults in the PATH Wave1 survey, 16% were daily users of cigarettes with the next most commonly used product being smokeless tobacco, at 1.8% of adults using daily.(2) A product standard for combustible tobacco products that limits the permissible nicotine content to a level that significantly reduces their addictiveness has the potential to significantly reduce the harms to public health from tobacco use in the United States.(3-5) The Family Smoking Prevention and Tobacco Control Act gave the FDA jurisdiction to implement such a product standard for cigarettes and other combustible tobacco products. The primary rationale for reducing the permissible nicotine content is to minimize the uptake and addictive use of cigarettes by new cohorts of young people.(6, 7) At the very least such a policy should not do harm to current smokers, particularly to vulnerable populations. A number of studies of reduced nicotine content cigarettes have now taken place and we have recently completed our own trials.(5, 8-10) However, very few trials to date have provided evidence on two key questions where gaps in our scientific knowledge remain. First, we do not know what the effects may be of immediate (as opposed to gradual) switching to VLNC cigarettes in SMHC. Second, when switching to VLNC cigarettes, no investigations have been conducted in a more realistic manner that enables systematic study of the effects of access to e-cigs. This trial will be significant and innovative as it will be the first ever randomized controlled trial to provide evidence of immediate switching to VLNC cigarettes in SMHCs while systematically studying the impact of access to e-cigs.

It has long been recognized that adults with mental health conditions are much more likely to smoke cigarettes than those without mental health conditions. Over time, those with mental health conditions are comprising a larger proportion of the remaining smokers.(11) For example, the current smoking prevalence among people without serious psychological distress fell from 20% in 2005 to 14% in 2015, whereas among people with serious psychological distress it stayed the same (42% vs. 41%) and actually increased for men.(12) The high smoking rates among people with mental health conditions is an important reason for large health disparities between people with serious mental health problems and those without, particularly in life expectancy.(13) Recent studies suggest that people with mental health conditions are similarly more likely to try, and to continue to use, e-cigs.(14, 15) For FDA to implement a reduced nicotine standard for combusted tobacco products it must possess reliable scientific data to estimate the likely public health effects in the real-world context of e-cig availability. In particular, FDA will need to know the health and addiction effects on SMHC. The proposed study will provide the data for this growing segment of the smoking population.

Over the past 10 years, e-cigs have become increasingly popular in the U.S. where more than 79% of U.S. adults are currently aware of the devices and 3.7% are using one on a regular basis.(16) Current every-day or someday e-cig use is most prevalent among current smokers (15.9%) and recent ex-smokers (22.0%) and is very uncommon among adult never cigarette smokers (0.4%).(16-18) E-cigs are battery-powered devices that heat and vaporize a liquid mixture (e-liquid), typically containing a vehicle such as propylene glycol (PG) and/or vegetable glycerin (VG) and often, but not always, nicotine and/or flavorings, to produce an aerosol that is inhaled by the user. E-cigs can expose users to several chemicals known to have adverse health effects including nicotine, carbonyls, and volatile organic compounds

(VOCs). The health effects of heated and aerosolized constituents of e-cig liquids, including solvents, flavors, and toxicants, are not completely understood.(19) However, some studies suggest e-cigs, when used exclusively, have a more favorable toxicity profile than tobacco cigarettes.(20, 21) E-cigs have become increasingly popular among cigarette smokers, particularly SMHC. For example, in the PATH Wave 1 survey, cigarettes plus e-cigs was by far the most common pattern of combined use.(2) In a large population survey from 2015, people with a mental health condition were twice as likely to be current cigarette smokers and twice as likely to be current e-cig users as people without a mental health condition.(14) This study aims to assess the likely health effects of a product standard lowering the nicotine content of cigarettes in SMHC when having access to e-cigs.

It is highly likely that in a scenario in which FDA issued a product standard requiring only very low nicotine content in cigarettes, existing smokers may attempt to supplement their nicotine from alternative sources. Given the current prevalence of e-cig use among current and former smokers, they are a prime candidate for such a source. To date, most studies designed to evaluate the likely effects of a low nicotine product standard for cigarettes have required participants to only use the specially designed reduced nicotine content cigarettes without supplementation from their own cigarettes or any other nicotine sources.(4, 8) This was a reasonable research design, however it has become clear that a significant proportion of those allocated to smoke only VLNC cigarettes were non-compliant, as their cotinine concentrations could not realistically be obtained from smoking only VLNC cigarettes.(22, 23) It seems most likely that the participants “topped off” their nicotine levels by occasionally smoking normal nicotine cigarettes. In the real world, if a product standard requiring only VLNC in cigarettes were to be implemented it is likely that alternate nicotine products, such as e-cigs, would also be available, so it is important to examine the patterns of product use and the resulting effects on biomarkers of toxicant exposure in that situation.

An initial feasibility trial of the reduced nicotine standard randomized smokers to 8 weeks of either NNC cigarettes or VLNC cigarettes and provided participants with access to alternative nicotine sources (either a variety of non-combusted products or a variety that included combusted products).(24) In this study, e-cigs were the most commonly selected alternative nicotine products used in all groups, and those allocated to VLNC cigarettes used more alternative products, had greater reductions in smoking rates and greater reductions in NNAL and exhaled CO compared with NNC cigarettes.(24) These results support the presumption that a reduced nicotine standard for cigarettes will likely lead to increased use of e-cigs and suggests that access to non-combusted nicotine products may enhance the effects of VLNC cigarettes leading to reduced smoking and toxicant exposure. The Donny and Hatsukami research group (CENIC) is currently preparing to implement two funded trials of reduced nicotine cigarettes in the context of alternative nicotine availability. However, there are no such trials focusing on the effects of VLNC cigarettes on smoking behavior and toxicant exposure specifically among SMHC, a vulnerable population that requires specialized investigations focused on how nicotine reduction may impact their mental health and smoking behavior. The current trial is designed to provide this much needed evidence.

